5.3 COMPUTING ENVIRONMENT

All statistical analyses will be performed using SAS statistical software Version 9.4 (or later), unless otherwise noted.

5.4 TIMING OF ANALYSES

Data will be analyzed as needed; the final analyses will be conducted after the last participant completes the last study assessment or withdraws from the study.

5.5 BASELINE DEFINITIONS

Baseline demographics and disease characteristics will be the baseline from both the parent study TDR14767(ALN-AT3SC-001) and study LTE14762. The following disease characteristics will be taken from the parent study:

- hemophilia type
- time since diagnosis
- biological phenotype
- prior treatment type
- historical ABR
- hepatitis C status
- historical ABR
- historical hemophilia clinic visit 6 months prior to parent study entry

Baseline assessment for by-visit analyses is defined as the last non-missing value on or before first significant Treatment Day and/or LTE14762 Study Day (ie, baseline on or before the first significant treatment day will be considered for all efficacy endpoints while baseline on or before the first LTE14762 study day will be considered for all safety endpoints). These baselines will be considered in analyses under both original and revised dose and regimen as main analysis.

An additional baseline under the revised dose and regimen is defined as the non-missing assessment on or prior to the revised dose re-start date regardless of dose regimen. It is applicable only for participant who consented to the protocol amendment 8. This baseline will be analyzed in selected safety endpoints under the revised dose and regimen. Detailed information will be specified in [Section 6.8](#).

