- c On Day 1, a directed physical examination will be performed at predose and 6 hours postdose. On all other dosing days checked in the table, the directed physical examination will be performed predose. See Section 9.1.5 for assessments to be performed during a directed physical examination.
- d Vital signs include blood pressure, heart rate, body temperature (oral, tympanic, or axillary), and respiratory rate. Vital signs will be measured in the seated or supine position after the patient has rested comfortably for 10 minutes. On Day 1, vital signs will be collected predose and at 6 hours (±30 minutes) postdose. On all other dosing days checked in the table, vital signs will be collected predose.
- e 12-lead ECGs will be performed in the supine position after the patient has rested comfortably for 10 minutes. 12-lead ECGs will be performed at predose; 30 minutes (±10 minutes) postdose; and 2, 4, and 24 hours (±30 minutes) postdose in relation to the Day 1 and Month 12 fitusiran doses. 12-lead ECGs will be performed at predose; 30 minutes (±10 minutes) postdose; and 2, 4, and 24 hours (±30 minutes) postdose in relation to the Month 24 fitusiran doses. At remaining visits checked in the table, the predose ECG will be performed before blood sample collection.
- f Full Hepatic Tests (Table 10) Sample must be performed in all patients once, at Screening (if newly enrolled) or at next scheduled clinic visit (if patient has already completed a clinic visit) and annually thereafter. FibroScan (or FibroTest with APRI) testing must be performed in all patients found to have positive hepatitis C antibody titers
- g As determined by Nijmegen modified Bethesda assay.
- h Blood samples will be collected predose at visits checked in the table. Biochemistry, hematology, and coagulation are described in Section 9.1.7.1. At Screening, only a complete blood count, platelet count, INR, and CD4 count in HIV seropositive patients is required; however, a CD4 count from the previous 6 months may be used to confirm eligibility.
- i Sample for urinalysis will be collected predose at visits checked in the table. Urinalysis parameters are described in Section 9.1.7.3.

- *j* Blood samples will be collected predose at visits checked in the table.

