10.2.6 Safety Analyses

Adverse events will be summarized by the MedDRA System Organ Class and Preferred Term. Incidence of treatment-emergent adverse events (TEAEs; those events that started after exposure to study drug or worsened in severity after dosing) will be presented by dose level and overall. Incidence of TEAEs will also be presented by maximum severity and relationship to study medication or underlying hemophilia. The incidence of SAEs and AEs leading to discontinuation of treatment will also be tabulated. By-patient listings will be provided for deaths, SAEs, and events leading to discontinuation of treatment.

Descriptive statistics will be provided for clinical laboratory data (including biochemistry, hematology, urinalysis, and coagulation) and vital signs data, presented as both actual values and changes from baseline relative to each on-study evaluation. Laboratory shift tables from baseline to worst values will be presented. Baseline will be defined as the last observation on or before Day 1. Abnormal physical examination findings, 12-lead ECG data, and antidrug antibody results will be presented in a by-patient data listing. Antidrug antibody results will also be tabulated.

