6.8.5 Electrocardiogram

Listings for 12-lead ECG will be provided. Additionally, PR, QRS, QT, Bazzett's (QTcB) and Fridericia's (QTcF) corrected QT and RR intervals will be summarized descriptively, where (QTcF) is calculated using the formula

$$QTcF \text{ (ms)} = QT \text{ (ms)} \cdot \sqrt[3]{\frac{HR \text{ (bpm)}}{60}}$$

and where (QTcB) is calculated using the formula

$$QTcB \text{ (ms)} = QT \text{ (ms)} \cdot \sqrt{\frac{HR \text{ (bpm)}}{60}}$$

For data under the original dose and regimen, the descriptive summary will be provided from the LTE14762 study baseline up to the 2017 clinical dose pause. For data under the revised dose, the summary will be provided from the dose resumption up to the end of study.

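### The main safety baseline is set by calendar day with no predose condition, so the rule as written takes a postdose Day 1 reading for vital signs (and for ECGs where they are summarised against baseline)

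*SAP*

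**What the plan says.** SAP 5.5 gives one rule for by-visit analyses: baseline is "defined as the last non-missing value on or before first significant Treatment Day and/or LTE14762 Study Day". It then assigns the extension-study anchor to safety: "baseline on or before the first LTE14762 study day will be considered for all safety endpoints". It makes these baselines the main analysis under both the original and the revised regimen. Protocol 10.2.6 agrees in substance: "Baseline will be defined as the last observation on or before Day 1".

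Protocol Table 1 places postdose measurements on that same day. Footnote d: "On Day 1, vital signs will be collected predose and at 6 hours (±30 minutes) postdose". Footnote e schedules ECGs predose, at 30 minutes, "and 2, 4, and 24 hours (±30 minutes) postdose in relation to the Day 1 and Month 12 fitusiran doses".

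On use, Protocol 10.2.6 promises "vital signs data, presented as both actual values and changes from baseline relative to each on-study evaluation". For ECG it plans a by-patient listing. SAP 6.8.5 adds descriptive summaries of the intervals, and for original-regimen data says "the descriptive summary will be provided from the LTE14762 study baseline up to the 2017 clinical dose pause".

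For the revised regimen, SAP 5.5 adds a second baseline, "defined as the non-missing assessment on or prior to the revised dose re-start date regardless of dose regimen", and refers to Section 6.8 for detail. Section 6.8 instead places this baseline before administration of the revised regimen, and applies it to laboratory, vital-sign and ECG endpoints.

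**The concern.** A change from baseline is meant to compare a later value with the state before the dose. If the reference is read 4 to 6 hours after the injection, any acute effect of that injection, and any time-of-day difference, enters the reference and is subtracted from every later change. Later vital signs are scheduled predose, so the comparison also mixes two positions in the dosing interval.

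Safety and tolerability are the primary objective, and vital signs and ECGs are listed safety variables. The 6-hour reading belongs to the first-dose observation period. Used as the reference, it no longer appears as a postdose finding in the change summaries.

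**Working it through.** No sample size, power or error rate is involved. The check applies the stated rule to the scheduled times and then looks for any text that overrides it.

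**Step 1: which Day 1 records qualify.** SAP 5.2 counts Study Days like Treatment Days: evaluation date minus first significant dose date, plus 1. A reading on the dosing date has Study Day 0 + 1 = 1 whatever the clock time. A 24-hour reading falls on the next date, so Study Day = 1 + 1 = 2.

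| Measure (Table 1) | Scheduled around the Day 1 dose | Qualifying (Study Day ≤ 1) | Last qualifying |
|---|---|---|---|
| Vital signs, footnote d | predose, +6 h | predose, +6 h | **+6 h postdose** |
| ECG, footnote e | predose, +0.5, +2, +4, +24 h | predose, +0.5, +2, +4 h | **+4 h postdose** |

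**Step 2: what the reference is compared with.** Table 1 takes vital signs predose on all other checked dosing days, and Table 2 takes them predose on its checked dosing days. The vital-sign comparison is therefore later predose against Day 1 postdose. For ECG, Months 12 and 24 repeat a postdose series; at the other checked Table 1 visits the tracing is predose.

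**Step 3: form of the error.** Let B be the Day 1 predose value, d the shift from predose to the selected postdose reading, and V a later predose value.

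- Change as planned: V − (B + d) = (V − B) − d.
- Error in the mean change: minus the mean of d, one unit for one unit, at every later visit.

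The documents give no value for d, so neither size nor sign can be stated.

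**Step 4: is there a predose limit elsewhere?**

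- PD baseline: before the first significant dose (SAP 6.4).
- QoL baseline: the Day 1 predose assessment (Protocol 10.2.3).
- Additional restart baseline: before administration (SAP 6.8).
- Main safety baseline for vital signs and ECG: none found. SAP 5.10 assigns visits from the CRF and gives no rule for several readings within one visit.

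Laboratory, urinalysis and antidrug-antibody samples are drawn predose in Table 1, so they are unaffected.

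**Step 5: the condition on Study Day 1.** SAP 5.2 starts Study Days at the first dose of at least 20 mg in LTE14762. SAP 2.1 has everyone starting at 50 or 80 mg, in which case Study Day 1 is the Day 1 visit and Step 1 applies. Protocol 6.5 expects a start at 0.225 mg/kg, and 20 mg ÷ 0.225 mg/kg = 88.9 kg, so below that weight the first dose would fall short of 20 mg. Study Day 1 would then be a later visit with predose vital signs only. The latest scheduled ECG before Month 12 would be the 24-hour tracing, still postdose. The share of such participants is not given.

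**Step 6: restart baseline.** Table 3 footnote d again schedules vital signs predose and 6 hours postdose on its Day 1. SAP 5.5, cut off by date, admits the 6-hour reading; SAP 6.8, cut off by administration, does not. SAP 5.5 also omits the word last here, so it does not say which qualifying value is used. Table 3 lists no postdose ECG series, so only vital signs are affected. Participants who restart at their prior monthly dose follow Tables 1 and 2 (Protocol 6.5.1.3) and have no scheduled 6-hour reading at restart.

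**The case against.** The strongest reply is that predose intent is visible wherever the documents elaborate on baseline (QoL, PD, restart), so a programmer would probably choose the predose record. The study is also open-label and descriptive with no powered hypothesis, and actual values are reported beside the changes. Original-regimen vital-sign and ECG summaries stop at the 2017 hold, and every participant had parent-study exposure, so this baseline was never drug-free.

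Much of this stands, and it lowers the severity. It does not remove the defect. Choosing the predose record would be an undocumented departure from both documents, and earlier exposure does not justify a same-day postdose reference.

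A reader might infer four stronger claims that the documents do not support:

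- **That change from baseline is planned for both vital signs and ECG.** It is explicit for vital signs only (Protocol 10.2.6). For ECG it is implied by the baseline-referenced wording of SAP 6.8 and 6.8.5.
- **That the restart baseline is postdose.** SAP 6.8 places it before administration. What remains is a mismatch with SAP 5.5.
- **That every participant is affected.** This depends on where the first dose of at least 20 mg falls, on which SAP 2.1 and Protocol 6.5 point different ways.
- **That later changes are understated by a known amount.** No passage reports an acute effect on blood pressure or ECG intervals.

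**Conclusion.** The point holds in this form. As written, the main safety baseline selects the 6-hour postdose vital signs wherever the Day 1 visit carries the first LTE14762 dose of at least 20 mg and the scheduled reading was taken. The planned vital-sign changes then compare later predose values with that reading. Under the same condition the rule selects the 4-hour postdose ECG, which has consequences only if intervals are summarised against baseline. Because SAP 5.5 uses this baseline as the main analysis in both periods, the effect carries into the revised-regimen summaries that use it. The restart baseline has two wordings that must be reconciled.

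The error in a mean change equals minus the mean postdose shift, of unknown size and direction. Severity is minor to moderate: the reference value is wrong as specified, but the summaries are descriptive, actual values are shown, and adverse events and laboratory data are untouched.

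**What to change.** 1. In SAP 5.5 and Protocol 10.2.6, define the safety baseline as the last non-missing value before the first fitusiran dose in LTE14762, by date and time, so that the predose record is used on Day 1.
2. In SAP 5.5, reword the restart baseline as the last non-missing value before the first post-pause dose, in line with SAP 6.8.
3. Summarise Day 1 postdose vital signs and ECGs as separate time points.
4. State in SAP 6.8.5 whether ECG intervals are summarised as change from baseline.

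The cost is a few sentences and a predose flag in the baseline derivation. No new data are needed, because Table 1 and Table 3 already schedule predose vital signs and Table 1 a predose ECG.

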5.6 RANDOMIZATION STRATIFICATION FACTORS

Not applicable.

5.7 MULTIPLE COMPARISONS/MULTIPLICITY

Not applicable.

5.8 MISSING DATA

Data will be analyzed as observed. No imputation for missing data will be performed, except in the case of missing questionnaire data and adverse event data. Missing questionnaire data will be handled according to universally accepted standards. If the assessment of the relationship to fitusiran is missing for an AE, this AE will be assumed as related to fitusiran. If the severity is missing for one of the treatment-emergent occurrences of an AE, the severity will be imputed with the maximal severity of the other occurrences. If the severity is missing for all the occurrences, the severity will be left as missing.

5.9 PROTOCOL DEVIATIONS

Major protocol deviations will be identified before final analysis.

5.10 DERIVED ANALYSIS VISIT WINDOWS

For LTE14762 by-visit analyses under the original dose and regimen such as lab and vital sign parameters, it is expected that all 002 study visits will occur according to the protocol schedule of assessments. Analysis visits will be assigned based on LTE14762 evaluation visits as recorded on the CRF even if the assessment is outside of the window for that study visit.

For TDR14767(ALN-AT3SC-001)/ LTE14762 combined by-visit analyses under the original dose and regimen such as PD and QoL endpoints, analysis visits will be defined as follows.

For participants whose first “significant” dose of fitusiran was administered in TDR14767(ALN-AT3SC-001) (eg, this could only occur in the MD cohort [Part C and Part D]; other cohorts are administered relatively small doses of fitusiran),

- a) Analysis visits for all TDR14767(ALN-AT3SC-001) assessments will be first assigned based on TDR14767(ALN-AT3SC-001) evaluation visit as recorded on the CRF and will be adjusted, if necessary, so that the window of the TDR14767(ALN-AT3SC-001) assessment overlaps as much as possible with the LTE14762 scheduling.
- b) Analysis visits will be derived for the LTE14762 Day 1 assessment based on the Treatment Days and will be assigned for subsequent visits based on LTE14762 evaluation visit as recorded on the CRF. For example, Haem-A-Qol is assessed quarterly in the 1st two years and then yearly after in LTE14762. If the Treatment Days for Day 1 visit is within 18 months +/-1.5 month, then analysis visit for Day 1 visit

will be derived as Month 18, and the subsequent analysis visits will be assigned quarterly or yearly after Month 18 accordingly.

For participants whose first “significant” dose of fitusiran was administered in LTE14762, Analysis visits under the original dose and regimen will be assigned based on LTE14762 evaluation visit as recorded on the CRF.

For LTE14762 by-visit analyses under the revised dose and regimen, analysis visits for scheduled visits will be defined based on CRF reported VISIT, even if the assessment is outside of the window for that study visit.

- For participant who had dose reduction after the dose pause, the analysis visit will be assigned based on the CRF reported PR VISIT (PRxx) as following example for the first 18 months after dose pause for the revised dose regimen scenarios. For unscheduled visit, the analysis visit will be populated based on treatment day after dose re-start (ie, Date of PR Day 1). The analysis visit window will be derived as the middle-point of the target day between the 2 consecutive scheduled visits for each of the assessment. The target day is calculated as 28 days of visit interval times corresponding scheduled months plus 1. The treatment day after the volunteer dose pause is defined in [Section 5.2](#)

Table 2 – Analysis visit schedule after the 2020 dose pause

CRF reported VISIT		Binning algorithm			
No dose escalation after pause	Dose escalated to 50QM	Analysis visit	Target day	Lower bound	Upper bound
50Q2M Day1	50Q2M Day1	PR Day 1	1	1	1
50Q2M PRM1	50Q2M PRM1	PR Month 1	29	2	42
50Q2M PRM2	50Q2M PRM2	PR Month 2	57	43	70
50Q2M PRM3	50Q2M PRM3	PR Month 3	85	71	98
50Q2M PRM4	50Q2M PRM4	PR Month 4	113	99	126
50Q2M PRM5	50Q2M PRM5	PR Month 5	141	127	154
50Q2M PRM6	50Q2M PRM6	PR Month 6	169	155	182
50Q2M PRM7	50QM PRM1	PR Month 7	197	183	210
50Q2M PRM8	50QM PRM2	PR Month 8	225	211	238
50Q2M PRM9	50QM PRM3	PR Month 9	253	239	266
50Q2M PRM10	50QM PRM4	PR Month 10	281	267	294
50Q2M PRM11	50QM PRM5	PR Month 11	309	295	322
50Q2M PRM12	50QM PRM6	PR Month 12	337	323	350
50Q2M PRM13	50QM PRM7	PR Month 13	365	351	378
50Q2M PRM14	50QM PRM8	PR Month 14	393	379	406
50Q2M PRM15	50QM PRM9	PR Month 15	421	407	434
50Q2M PRM16	50QM PRM10	PR Month 16	449	435	462
50Q2M PRM17	50QM PRM11	PR Month 17	477	463	490
50Q2M PRM18	50QM PRM12	PR Month 18	505	491	518

- For participant who remain the original dose regimen after the dose pause, the analysis visit will be derived based on original visit schedule (ie, Month xx), which will be reported following the original visit scheme. The first dose date after the dose pause will be assigned as Day1. The subsequent visits can be assigned based on the first visit accordingly. For example, the first visit after dose re-start is reported as “Month 36”, then the next visit is reported as “Month 37”. The Month 36 visit should be assigned as “PR Day 1” and the Month 37 should be assigned as “PR Month 1”. For unscheduled visit, the analysis visit will be populated based on treatment day after dose re-start. The analysis visit window will be derived as the middle-point of the target day between the 2 consecutive scheduled visits for each of the assessment. The target day is calculated as 30 days of visit interval times corresponding scheduled months plus 1. The treatment day after the volunteer dose pause is defined in [Section 5.2](#).

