- a This schedule applies for patients meeting criteria for adjusted dosing regimen. Upon each dose adjustment, the patient will restart the schedule (For dose adjustment from 50 mg Q2M to 50 mg QM, the patient will restart at PR M1 as their Month 6 visit under 50 mg will serves as their PR Study Day 1. For dose adjustment from 50 mg QM to 80 mg QM, the patient will restart at PR Study Day 1). The duration that the patient must continue in the study post modified IMP dose/frequency re-start depends on the re-start time-point relative to the overall study start for each individual patient to ensure an overall duration of fitusiran administration of approximately 72 months or 18 calendar months after restarting dosing post dosing pause (whichever is longer). Thus, when the patient reaches the latter of 72 months of study participation or 18 calendar months post dosing restart, the EOT visit should be performed, followed by the EOS and AT follow-up period.
- b Patients will follow either the Q2M or QM dosing regimen according to the dose adjustment rules; see Section 6.5.1.3. SC administration of study drug as per Pharmacy Manual. From Year 3 onwards, the frequency of predose LFT monitoring may be decreased for patients who have negative hepatitis C antibody titers and meet specific criteria defined in Section 6.5.1.1.
- c On Day 1, a directed physical examination will be performed at predose and 6 hours postdose. On all other dosing days checked in the table, the directed physical examination will be performed predose. See Section 9.1.5 for assessments to be performed during a directed physical examination.
- d Vital signs include blood pressure, heart rate, body temperature (oral, tympanic, or axillary), and respiratory rate. Vital signs will be measured in the seated or supine position after the patient has rested comfortably for 10 minutes. On Day 1, vital signs will be collected predose and at 6 hours (±30 minutes) postdose. On all other dosing days checked in the table, vital signs will be collected predose.
- e 12-lead ECGs will be performed in the supine position after the patient has rested comfortably for 10 minutes. 12-lead ECGs will be performed before blood sample collection.

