6.5.1.3 Antithrombin level criteria for a dose adjustment

With the introduction of the new dose and regimen with Protocol Amendment 07 following the global program dosing pause implemented by Sponsor in 2020, patients will receive fitusiran treatment according to the below antithrombin level scenarios and criteria. See the rationale for a new dosing justification in Section 1.5. Dose modification rules are detailed in the section below and displayed in Figure 1 and Figure 2.

A) Dose restart

- a) Restart at 50 mg Q2M
- Patients that reach AT activity levels ≥22% (per central laboratory),
- Patients previously exposed to fitusiran at a dose of 50 mg QM or 80 mg QM with more than one AT activity level <15% (per central laboratory) at any time during fitusiran treatment,
- Patients will resume dosing at a dose of 50 mg Q2M and follow the modified IMP regimen SoAs (Table 3).
- b) Restart at 50 mg QM or 80 mg QM (prior dose)
- Patients that reach AT activity levels ≥22% (per central laboratory),
- Patients previously exposed to fitusiran at a dose of 50 mg QM or 80 mg QM with no more than one AT activity level <15% (per central laboratory) at any time during fitusiran treatment (based on at least 3 months of prior AT measurements),
- Participant may have the option to remain on that dose and follow the SoAs in Table 1 and Table 2.

B) Dose escalation

- a) Dose escalation to 50 mg QM
- After a period of dosing at 50 mg Q2M,
- Based on 2 steady state AT values >35% at the 50 mg Q2M dosing regimen,

- At least 2 of the 3 AT samples taken pre-dose at PR Month 4, PR Month 5 and PR Month 6 must be >35% to meet the escalation rule,
- Patients who previously had more than 1 AT value <15% at the 50 mg QM dose are not eligible to re-escalate to this dose level,
- If escalation rules are met, patient will receive the 50 mg dose at PR Month 7 (this will be considered the PR Month 1 of 50 mg QM, ie, the second 50 mg QM dose).

Note: If any of the doses prior to PR Month 6 are missed, then the decision-making for escalation must be shifted accordingly.

- b) Dose escalation to 80 mg QM
- After a prior escalation to the 50 mg QM dosing regimen,
- Based on 2 steady state AT values >35% at the 50 mg QM dosing regimen,

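### SAP 5.10 takes revised-regimen visits from a CRF label that restarts at each dose adjustment, and Table 2 corrects the restart only for escalation to 50 mg QM at PR Month 6

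*SAP*

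**What the plan says.** SAP 5.10 states that under the revised regimen "analysis visits for scheduled visits will be defined based on CRF reported VISIT", even when the assessment lies outside its window. It then adds: "For participant who had dose reduction after the dose pause, the analysis visit will be assigned based on the CRF reported PR VISIT (PRxx", and Table 2 is introduced "as following example for the first 18 months after dose pause for the revised dose regimen scenarios". Table 2 has two scenario columns: no escalation, and "Dose escalated to 50QM". In the second, 50QM PRM1 to PRM12 become PR Months 7 to 18.

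Unscheduled visits are handled differently. They are binned by treatment day since the dose restart, which SAP 5.2 counts from the first dose after the pause.

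Participants who stay on their monthly regimen have their own scheme at the end of SAP 5.10, with 30-day targets: "The first dose date after the dose pause will be assigned as Day1".

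Protocol Table 3, footnote a, governs the CRF label: "Upon each dose adjustment, the patient will restart the schedule". Protocol 6.5.1.3 allows resets at times other than PR Month 6:
- **Shifted escalation:** "If any of the doses prior to PR Month 6 are missed, then the decision-making for escalation must be shifted accordingly".
- **Later escalation:** item B) c) lets criteria be met later, using any steady-state central AT result.
- **80 mg QM:** item B) b) makes PR Month 4 of 50 mg QM the new PR Day 1.
- **Reduction:** item C) c) moves a QM restarter with more than one AT level below 15% to 50 mg Q2M, no sooner than 2 months after the last QM dose.

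**The concern.** Table 2 shows that the SAP intends a cumulative count from the post-pause restart. The label it reads counts from the most recent dose adjustment. The two agree only where Table 2 has a row that undoes the reset.

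On the other permitted paths, a by-visit summary would mix different times since restart. It could also hold two records from one participant under one visit, taken on different regimens. SAP 5.10 has no rule for choosing between them. AT itself triggers most of these adjustments, so the misplaced records are not a random subset. With at most 48 participants enrolled, a few such records can shift a by-visit mean.

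The outputs at stake are the by-visit PD, QoL and laboratory summaries, and vital signs or ECG where shown by visit.

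**Working it through.** **Reproducing Table 2.** The target day is 28 × month + 1. Window bounds are midpoints between consecutive targets, and PR Month 1 opens on Day 2. All 18 monthly rows reproduce exactly; for example, PR Month 7 is Day 197 (183–210) and PR Month 9 is Day 253 (239–266).

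**Escalation at PR Month 6.** 50QM PRMk falls on Day 28 × (6 + k) + 1, which is PR Month 6 + k. This is what Table 2 assigns, so there is no error.

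**Shifted or late escalation.** Let the decision fall at PR Month E (assumed), with the next visit recorded as 50QM PRM1. Its true day is 28 × (E + 1) + 1. Table 2 gives it PR Month 7, target Day 197. The displacement is 28 × (E − 6) days.

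| E (assumed) | True day of 50QM PRM1 | True visit | Assigned visit | Days early | Labels used twice |
|---|---|---|---|---|---|
| 8 | 253 | PR Month 9 | PR Month 7 | 56 | PR Months 7–8 |
| 10 | 309 | PR Month 11 | PR Month 7 | 112 | PR Months 7–10 |
| 12 | 365 | PR Month 13 | PR Month 7 | 168 | PR Months 7–12 |
| 14 | 421 | PR Month 15 | PR Month 7 | 224 | PR Months 7–14 |

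A doubled label yields two values only for assessments scheduled at both visits. For AT and TG, Protocol Table 3 is monthly through PRM12 and sparser after that.

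**Two clocks.** With E = 8, the scheduled sample on Day 253 is labelled PR Month 7. An unscheduled sample five days later, on Day 258, falls in 239–266 and is labelled PR Month 9.

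**QM restarter later reduced to 50 mg Q2M.** Take a month as 30 days (Protocol 1.5) and put the last QM dose at month j (assumed), Day 30j + 1. The first Q2M dose is then no sooner than about Day 30j + 61. If the CRF records it as 50Q2M Day1, Table 2 makes it PR Day 1, which is 30j + 60 days early.

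| j (assumed) | Earliest 50Q2M Day 1 | Days early |
|---|---|---|
| 0 | 61 | 60 |
| 1 | 91 | 90 |
| 3 | 151 | 150 |
| 6 | 241 | 240 |

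The participant already has a PR Day 1 and later PR visits under the 30-day scheme, so those labels recur. The permitted visit window can shorten the gap slightly. The requirement that AT recover to at least 22% can lengthen it.

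**80 mg QM.** If every step is on time, 80QM Day 1 is 50QM PRM4, which is PR Month 10, Day 281. Table 2 has no row for it, so the analysis visit is undefined.

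**The case against.** The strongest reply is that Table 2 is offered as an example, already shows a cumulative count, and is exact for the non-escalated and the on-time 50 mg QM participants. That stands. A reader might infer that the SAP uses the raw restarting label throughout; it does not. But no other rule covers the remaining paths, so a programmer must either follow the label or improvise.

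A reader might also infer that participants escalated to 80 mg QM are placed months early and counted twice. The documents do not support this. Table 2 labels carry a regimen prefix, and nothing maps an 80 mg label to PR Day 1. The exclusions in Protocol 6.5.1.3 also leave few participants who could reach that dose, and Protocol 1.5 calls such cases very rare.

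The reduction case rests on an inferred CRF label. Footnote a restarts the schedule at each adjustment but spells out only the two escalation steps. SAP 5.10 does not clearly say whether a QM restarter reduced later belongs to the dose-reduction paragraph or to the one on remaining at the original regimen.

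The reach is also limited. The protocol calls later escalation rare, although it attaches no such word to the reduction in C) c). ABR and bleed-free duration work from dates. Post-pause PD is presented by treatment sequence (SAP 6.4). That separates some groups, but on-time and late escalators share a sequence, and it does not remove duplicates within a participant.

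Finally, it is tempting to re-bin every post-pause visit with the Table 2 windows. That would do harm. An on-schedule QM restarter's Month 7 is Day 30 × 7 + 1 = 211, which falls in the 28-day PR Month 8 window (211–238).

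**Conclusion.** The point holds in a limited form. For escalation after PR Month 6, the written rule gives a wrong analysis visit: 56 days early for a decision at PR Month 8, and 112 to 224 days for PR Months 10 to 14, with repeated labels. For a QM restarter reduced to 50 mg Q2M, the displacement is at least about 60 days, conditional on the CRF label restarting. For 80 mg QM the gap is a missing mapping, not a demonstrated error.

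The decision months and last-dose months are assumptions. The documents do not give the number affected, which is probably small. The consequence is confined to descriptive by-visit summaries. It should be corrected, but it does not threaten the bleeding analyses.

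**What to change.** Amend SAP 5.10 as follows:
- Keep Table 2 for non-escalated participants and for those escalated to 50 mg QM at PR Month 6.
- Keep the 30-day scheme for QM restarters while they stay on that regimen.
- After any other schedule reset (shifted or late escalation, 80 mg QM, reduction to Q2M), assign scheduled visits on the same clock as unscheduled ones: treatment day since the first post-pause dose (SAP 5.2). Use assessment-specific windows extended to the end of follow-up, since Table 2 stops at PR Month 18 and Protocol Table 3 runs to PRM36.
- On those paths, use the CRF label only to identify dose and regimen at sampling.
- State one rule for several records in a window, for example the scheduled record closest to the target day.

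The cost is SAP wording and minor programming. No new data are needed.
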